6.2.2 Physical Exams and Vital Signs

Physical exams and vital signs will be performed as indicated in the Schedule of Procedures ([Appendix A](#)). Vital signs should include weight, blood pressure (BP), pulse rate, respiratory rate and body temperature. BP and pulse rate will be recorded after the patient has been in a sitting position for at least 5 minutes. BP should always be measured on the same arm (preferentially on the left arm). Height will be measured at Screening.

6.2.3 Electrocardiography

Electrocardiography (ECG) will be conducted at Screening, Day 1, (prior to the first dose of Study Drug), and again during the treatment period as follows per dosing cohort:

- Cohorts A and B at Weeks 5, 13, 21, 25, 33, 41, 49, and 53
- Cohorts C and D at Weeks 5, 13, 21, 25, 27, 33, 41, 49, and 53

Patients assigned to the PK Subgroup will have additional ECGs conducted as indicated in the Schedule of Procedures ([Appendix A](#)). In all cohorts, ECGs will be conducted during the post-treatment follow-up period as outlined in [Appendix A](#).

ECGs will be recorded after the patient has been resting in a supine position for at least 5 minutes. ECGs will be performed in triplicate.

6.2.4 PK Sampling

Blood samples for the determination of plasma ISIS 678354 concentrations will be collected prior to dosing on Day 1 and at various times throughout the treatment and post-treatment follow-up periods as noted in the tables in [Appendix C](#).

Within each cohort, patients assigned to the PK Subgroup will have additional PK sampling time points and additional visits to the clinic during the treatment period in order to collect blood samples for PK assessment ([Appendix C](#)).

6.3 Restriction on the Lifestyle of Patients

6.3.1 *Contraception Requirements*

All male patients and women of childbearing potential must refrain from sperm/egg donation and either be abstinent[†] or practice effective contraception from the time of signing the informed consent form until at least 13 weeks after their last dose of study treatment.

Male patients engaged in sexual relations with a female of child-bearing potential must also encourage their female partner to use effective contraception from the time of signing the informed consent until 13 weeks after the patient's last dose of study treatment.

For the purposes of this study, women of childbearing potential are defined as any female who has experienced menarche, and who does not meet 1 of the following conditions:

- Postmenopausal: 12 months of spontaneous amenorrhea in females > 55 years of age or, in females ≤ 55 years, 12 months of spontaneous amenorrhea without an alternative medical cause and FSH levels in the postmenopausal range for the laboratory involved
- 6 weeks after surgical bilateral oophorectomy with or without hysterectomy
- Post hysterectomy

For the purposes of the study, effective contraception is defined as follows:

For male patients:

- Effective male contraception includes a vasectomy with negative semen analysis at Follow-up, or the use of condoms together with spermicidal foam/gel/film/cream/suppository
- Male patients with partners that are pregnant must use condoms as contraception to ensure that the fetus is not exposed to the Study Drug

For female patients and female partners of male patients:

- Using 2 of the following acceptable methods of contraception: surgical sterilization (e.g., bilateral tubal ligation), hormonal contraception, intrauterine contraception/device, or any 2 barrier methods (a combination of male or female condom* with diaphragm, sponge, or cervical cap) together with spermicidal foam/gel/film/cream/suppository

†Note: Abstinence is only acceptable as true abstinence, i.e., when this is in line with the preferred and usual lifestyle of the patient. Periodic abstinence (e.g., calendar, ovulation, symptothermal, post-ovulation methods), declaration of abstinence for the duration of a trial and withdrawal are not acceptable methods of contraception.

***Note:** A female condom and a male condom should not be used together as friction between the 2 can result in either or both products failing.

6.3.2 *Other Requirements*

All patients will be required to fast for at least 10 hours and preferably not more than 12 hours before visits requiring fasted blood sampling.

7. STUDY DRUG

7.1 Study Drug Description

Study Drug (ISIS 678354 or Placebo) characteristics are listed in [Table 1](#).

Study Drug (ISIS 678354 or Placebo) will be provided as 0.8 mL deliverable volume in 2 mL stoppered and sealed glass vials as a sterile solution.

The Study Drug is clear to slightly yellow in color, it is for single use, contains no preservatives and must be stored between 2 to 8 °Celsius and be protected from light.

7.1.1 *ISIS 678354*

ISIS 678354 vials contain 100 mg/mL ISIS 678354 in Water for Injection. Additionally, sodium phosphate buffer and sodium chloride are added to control the measure of the acidity or basicity of the solution (pH) and tonicity, respectively. The target pH is 7.4.

7.1.2 *Placebo*

Placebo vials contain 0.9% sodium chloride in Water for Injection. 1.6 µg/mL riboflavin is added to ensure color matching of placebo vials to ISIS 678354 vials.

Table 1 Study Drug Characteristics

Study Drug	ISIS 678354	Placebo
Strength	100 mg/mL	Not Applicable
Volume/Formulation	0.8 mL solution per 2.0 mL vial	0.8 mL solution per 2.0 mL vial
Route of Administration	SC	SC

SC = subcutaneous

7.2 Packaging and Labeling

The Sponsor will provide the Investigator with packaged Study Drug (ISIS 678354 or placebo) labeled in accordance with specific country regulatory requirements.

7.3 Study Drug Accountability

The study staff is required to document the receipt, dispensing, and return of Study Drug (ISIS 678354 or placebo) supplies provided by the Sponsor. The patient must return all used and unused Study Drug to the Study Center for accountability. The Study Center must return all used and unused Study Drug to the Sponsor or designee for destruction. All used syringes must be disposed of as per the site's hazardous waste destruction policy.

8. TREATMENT OF PATIENTS

8.1 Study Drug Administration

ISIS 678354 will be administered to patients by Study Center staff as follows:

Cohort A: a single SC dose of 10 mg once every 4 weeks for up to 49 weeks and a maximum of 13 doses

Cohort B: a single SC dose of 50 mg once every 4 weeks for up to 49 weeks and a maximum of 13 doses

Cohort C: a single SC dose of 15 mg every 2 weeks for up to 51 weeks and a maximum of 26 doses

Cohort D: a single SC dose of 10 mg every week (weekly) for up to 52 weeks and a maximum of 52 doses

Self-administration will be allowed after appropriate training of patient and/or caregiver.

Patients in Cohorts A and B should receive 1 dose every 4 weeks, patients in Cohort C should receive 1 dose every 2 weeks and patients in Cohort D should receive 1 dose per week, with weeks always defined relative to Study Day 1. For example, if a patient receives the first dose on a Monday, subsequent doses should be given on Mondays according to the respective dosing schedule, if possible. If a patient misses an injection, or if dosing on the usual day is not possible, the patient can reschedule the injection provided that 2 doses are administered at least 2 days apart.

Every effort should be made to ensure the previous dose is given 7 days prior to a scheduled clinic visit.

Please refer to the Study Drug Manual provided by the Sponsor or designee for more detailed instructions for Study Drug (ISIS 678354 or placebo) preparation and administration.

Table 2 Study Drug Dosing Information

Cohort	Treatment	Volume to Administer/Dose	# Doses	Total ISIS 678354
A	10 mg ISIS 678354 or placebo (Every 4 weeks)	0.10 mL	≤ 13	≤ 130 mg
B	50 mg ISIS 678354 or placebo (Every 4 weeks)	0.50 mL	≤ 13	≤ 650 mg
C	15 mg ISIS 678354 or placebo (Every 2 weeks)	0.15 mL	≤ 26	≤ 390 mg
D	10 mg ISIS 678354 or placebo (Every week)	0.10 mL	≤ 52	≤ 520 mg

8.2 Other Protocol-Required Drugs

No other Study Drug treatments are required by the protocol.

8.3 Other Protocol-Required Treatment Procedures

No other treatment procedures are required by the protocol.

8.4 Treatment Precautions

No specific treatment precautions are required.

8.5 Safety Monitoring Rules

Stopping rules are described below in [Section 8.6](#).

Please refer also to the “Guidance for Investigator” section of the Investigator’s Brochure.

For the purposes of safety monitoring Baseline is defined as the average of the pre-dose test closest to Day 1 and the Day 1 value itself.

In addition to the standard monitoring of clinical safety parameters, the following guidelines are provided for the monitoring of selected parameters chosen based on preclinical and clinical observations.

In case of discrepancy between the test results from 2 sources, such as between the central and local lab, safety-mandated action must be initiated based on the more critical (lower or higher, as relevant) of the 2 values.

Confirmation Guidance: At any time during the study (treatment or post-treatment follow-up periods), the clinical laboratory results meeting any of the safety monitoring criteria presented below must be confirmed by performing measurements (ideally in the same laboratory that performed the initial measurement) on new specimens prior to administering the next dose of Study Drug (ISIS 678354 or placebo). All new specimen collections should take place as soon as possible (ideally within 3 days of the initial collection).

In addition, as described in [Section 6.2.1](#) hematology labs should be sent in parallel to the central and local laboratory for analysis.

Stopping Rule Guidance: The Investigator may interrupt or permanently discontinue study treatment for any medical reason including changes in clinical laboratory results.

In the event of an initial clinical laboratory result that meets a stopping criterion, study drug must not be administered again until a confirmatory test result has been reviewed by the Study Medical Monitor. If any of the stopping criteria described below (refer to [Sections 8.6.1](#) to [8.6.3](#)) are met and are confirmed, the patient will be permanently discontinued from further treatment with Study Drug (ISIS 678354 or placebo), evaluated fully as outlined below and in consultation with the Study Medical Monitor or appropriately qualified designee, and will be entered into the post-treatment evaluation portion of the study. In general, patients who do not meet the stopping rules based upon retest may continue dosing. However, the Investigator and the Study Medical Monitor (or appropriately qualified designee) should confer as to whether additional close monitoring of the patient is appropriate.

Additional Guidance: If possible, a PK sample should be collected as soon as possible after an SAE has occurred (preferably within 2 weeks). In addition, if a patient is asked to return to the clinic for additional evaluations due to an AE, then a PK sample should be taken at the time of the unscheduled visit.

8.5.1 Safety Monitoring Rules for Liver Chemistry Tests

The following rules are adapted from the FDA guidance for industry, “Drug-Induced Liver Injury: Premarketing Clinical Evaluation,” issued by the U.S. Department of Health and Human Services, Food and Drug Administration, July 2009. For a definition of Baseline, please refer to guidance in [Section 8.5](#) above.

All patients will have liver chemistry tests monitored every 14 days (± 2 days) for the first 3 months of the study treatment, and monthly thereafter during the Treatment Period. Upon completion of the study treatment period, liver chemistry tests should be monitored as per visit schedule in [Appendix A](#).

In the event of appearance of symptoms or signs of hepatic injury (jaundice, fatigue, nausea, vomiting, right upper quadrant pain or tenderness, fever, rash, abnormal bleeding or bruising, or eosinophilia $>$ ULN) liver enzymes and bilirubin should be tested as soon as possible. Testing at a lab that is local to the patient is permissible for this purpose.

In the event of an ALT or AST measurement that is $> 3 \times$ ULN (or the greater of $2 \times$ baseline value or $3 \times$ ULN if the baseline value was $>$ ULN) at any time during the study (treatment or post-treatment period), the initial measurement(s) should be confirmed as described in [Section 8.5](#).

Patients with confirmed ALT or AST levels $> 3 \times$ ULN should have their liver chemistry tests (ALT, AST, ALP, international normalized ratio [INR] and total bilirubin) retested at least once-weekly until ALT and AST levels become $\leq 1.2 \times$ ULN.

All results of liver function tests must be reviewed promptly (within 48 hours of receipt) by the Investigator or the designee to ensure that the result has not met the stopping rules per [Section 8.6.1](#).

Further Investigation into Liver Chemistry Elevations: For patients with confirmed ALT or AST levels $> 3 \times \text{ULN}$, the following evaluations should be performed:

1. Obtain a more detailed history of symptoms and prior and concurrent diseases
2. Obtain further history for concomitant drug use (including nonprescription medications, herbal and dietary supplement preparations), alcohol use, recreational drug use, and special diets
3. Obtain a history for exposure to environmental chemical agents and travel
4. Serology for viral hepatitis (hepatitis A virus [HAV] immunoglobulin M [IgM], hepatitis B surface antigen [HBsAg], hepatitis C virus [HCV] antibody, Cytomegalovirus [CMV] IgM, and EBV antibody panel)
5. Serology for autoimmune hepatitis (e.g., antinuclear antibody [ANA])

Additional liver evaluations, including gastroenterology/hepatology consultations, hepatic CT or MRI scans, may be performed at the discretion of the Investigator, in consultation with the Sponsor Medical Monitor and the study DSMB. Repetition of the above evaluations should be considered if a patient's ALT and/or AST levels reach $5 \times \text{ULN}$.

All routine liver function test results will be reviewed on an ongoing basis at the weekly safety review by the Medical Monitor.

All lab alerts for abnormal liver function tests must be promptly reviewed by the Investigator (within 48 hours of receipt) and Medical Monitors (within 24 hours of receipt).

Lab alerts for abnormal liver chemistry tests will be issued for: 1) ALT or AST $> 3 \times \text{ULN}$; 2) ALT or AST $> 2 \times \text{baseline}$; 3) total bilirubin $> \text{ULN}$; 4) ALP $> \text{ULN}$. These alert levels are set to anticipate the risk of a combined elevation of aminotransferases and bilirubin as per the FDA Guidance referenced in [Section 8.5.1](#).

8.5.2 Safety Monitoring for Renal Function

While on treatment all patients will have renal function tests monitored every 14 days (± 2 days) for the first 3 months of the study treatment, and monthly thereafter during the Treatment Period. Upon completion of the study treatment period, urine renal biomarkers will be monitored as per visit schedule in [Appendix A](#).

In the event of appearance of symptoms or signs consistent with renal dysfunction such as hematuria, polyuria, anuria, flank pain, new-onset hypertension, nausea and/or anorexia, renal function should be tested as soon as possible. Testing at a lab that is local to the patient is permissible for this purpose.

While on treatment during the course of the study, urinary surveillance will include urinalysis to include urine albumin/creatinine ratio (UACR), urine protein/creatinine ratio (UPCR) and

urinary red blood cells (RBCs), as well as serum creatinine and cystatin-C which will be monitored every 14 days (± 2 days). In addition, biomarkers of acute renal injury will also be measured every 14 days (± 2 days) ([Appendix B](#)).

The assessment of serum creatinine, cystatin-C, and urinalysis more frequently than every 14 days will be guided by consultation with a local nephrologist. Any decision taken by the Investigator to discontinue study medication will be made taking into account all available and relevant data. In addition, the decision to discontinue Study Drug may also be based on lesser changes in these parameters observed in isolation or in association with other renal-related abnormalities. Any decision taken to restart study medication will be made in consultation with the Study Medical Monitor taking into account all available and relevant data.

All renal function test results will be reviewed on an ongoing basis by the Medical Monitor.

All results of renal function tests must be reviewed promptly (within 48 hours of receipt) by the Investigator or the designee to ensure that the result has not met the stopping rules per [Section 8.6.2](#).

Lab alerts for abnormal renal tests will be issued for:

- estimated GFR (eGFR) (by CKD-EPI formula) decrease from Baseline $> 25\%$,
- urine albumin/creatinine ratio (UACR) $> 250 \text{ mg/g}$,
- urine protein/creatinine ratio (UPCR) $> 0.5 \text{ mg/mg}$, or
- increase in serum creatinine from Baseline $> 0.3 \text{ mg/dL}$

These alert levels are set to anticipate and prevent the risk of a medically significant change in renal function while receiving Study Drug. If any of the above criteria are met, treatment should immediately be interrupted, and the Study Medical Monitor should be informed. In addition, the result should be confirmed as soon as possible (as described in [Section 8.5](#)), but no later than 7 days after the initial event. If the confirmatory test is negative (i.e. repeat sample taken within 7 days is within normal limits), the patient may continue treatment upon consultation with the Study Medical Monitor.

The Investigator should also review the patient's concomitant medications for potentially nephrotoxic agents, and, with the results of these evaluations, review any decision to continue or discontinue the patient in consultation with the Study Medical Monitor and the medical area specialist consultant of the DSMB.

Further instruction regarding treatment interruption and/or permanent stopping of study drug can be found in [Section 8.6.2](#).

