8.6.2 Stopping Rules for Renal Function Test Results

In the event that any of the renal monitoring rules summarized in [Section 8.5.2](#) are met, treatment should immediately be interrupted and the abnormal result should be confirmed as soon as possible, but no later than 7 days after the initial event. In addition, upon consultation with the Study Medical Monitor, site will obtain any additional lab assessments necessary to determine any alternative etiologies that may account for the abnormal result. If results from additional testing confirm the initial abnormal lab result, future treatment of the patient will be determined per the guidelines below:

- An alternative etiology is identified that may account for abnormal results:
 - Patient will have treatment interrupted until either:
 - Lab values have returned to baseline, and/or
 - Alternative etiology has resolved/recovered, AND
 - Study Medical Monitor has approved treatment to resume
- An alternative etiology has not been identified that may account for abnormal results:
 - Patient will be permanently withdrawn from treatment

The follow-up schedule and frequency of renal function monitoring after the initial event will be determined by the Study Medical Monitor in consultation with the Investigator and the medical area specialist on the DSMB. The Investigator should consider consulting a local nephrologist for any change of renal function that presents a concern. If a renal biopsy is performed, a sample specimen should be made available for examination by an independent renal pathologist who has been engaged by the Sponsor to review such specimens.

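### A renal alert triggered by a change from Baseline can be cleared by a repeat that is merely within normal limits, so dosing may resume while the alert is still met

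*Combined protocol and SAP*

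**What the plan says.** Protocol section 8.5.2 lists four renal alerts. Two are relative to the patient's own starting value: "estimated GFR (eGFR) (by CKD-EPI formula) decrease from Baseline" of more than 25%, and "increase in serum creatinine from Baseline" of more than 0.3 mg/dL. The other two are absolute levels: UACR above 250 mg/g and UPCR above 0.5 mg/mg.

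Meeting any alert interrupts dosing at once, and the result must be confirmed within 7 days. When that repeat comes back "negative (i.e. repeat sample taken within 7 days is within normal limits), the patient may continue treatment upon consultation with the Study Medical Monitor".

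Safeguards are also given. Section 8.5.2 says that "the decision to discontinue Study Drug may also be based on lesser changes in these parameters observed in isolation", that a restart takes account of all relevant data, and that decisions to continue or discontinue are reviewed "in consultation with the Study Medical Monitor and the medical area specialist consultant of the DSMB".

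Section 8.6.2 starts from the same alerts: "If results from additional testing confirm the initial abnormal lab result, future treatment of the patient will be determined per the guidelines below". If another cause is found, dosing stays interrupted until values are back to baseline and/or the cause has resolved, and the Medical Monitor approves. If none is found, the patient is permanently withdrawn. The section does not define what counts as confirming.

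**The concern.** The trigger and the release use different yardsticks. A creatinine or eGFR value can be unremarkable for the population and still be a large change for that patient, and large change is what these two alerts are meant to detect. Section 8.5.2 nevertheless calls such a repeat negative.

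The same repeat is most naturally read as confirmed under 8.6.2, where an unexplained result leads to permanent withdrawal. Two sites could therefore handle identical results differently: one resumes dosing, the other withdraws the patient. At stake are:

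- the patient's continued exposure;
- expedited reporting, because events meeting the 8.6.2 criteria are adverse events of special interest (protocol 9.3.3.1);
- the SAP 3.7.4 count of patients stopped under a rule.

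There is also an imbalance. A change with an identified cause must meet the 8.6.2 conditions for resuming, while an unexplained change that persists can be released under 8.5.2 on a normal-limits result after consultation.

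**Working it through.** **Inputs.** The alert thresholds are from protocol 8.5.2. Entry excludes eGFR below 60 (5.2), so patients with high baselines are eligible. The documents give no reference ranges. I assume a lower eGFR limit of 60 or 90 mL/min/1.73 m² and an upper creatinine limit of 1.0, 1.1, 1.2 or 1.3 mg/dL.

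**eGFR.** A fall above 25% can stay within limits when 0.75 × baseline > lower limit, that is, when baseline > limit/0.75. The largest fall that can be called negative is 1 − limit/baseline.

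| Assumed lower limit | Baselines affected | Largest fall called negative |
|---|---|---|
| 60 | above 60/0.75 = 80 | 1 − 60/90 = 33%; 1 − 60/100 = 40%; 1 − 60/110 = 45% |
| 90 | above 90/0.75 = 120 | 1 − 90/125 = 28% |

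Example: 100 to 74 is 74/100 − 1 = −26%. The alert is met, and the value is normal if the limit is 60.

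**Creatinine.** A rise above 0.3 can stay within limits when baseline < upper limit − 0.3.

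| Assumed upper limit (mg/dL) | Baselines affected | Largest rise called negative at baseline 0.70 |
|---|---|---|
| 1.0 | below 0.7 | 0.30 (does not exceed the alert) |
| 1.1 | below 0.8 | 0.40 |
| 1.2 | below 0.9 | 0.50 |
| 1.3 | below 1.0 | 0.60 |

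Examples: 0.60 to 0.95 (+0.35) meets the alert and is normal under all four limits. 0.70 to 1.05 (+0.35, or +50%) is normal for limits 1.1 to 1.3 but not 1.0.

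These are single-analyte bands. If both analytes must be normal, fewer patients are affected; I have not computed that overlap.

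**The opposite direction.** The normal-limits test is sometimes the stricter one:

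- eGFR 62 to 47 is 47/62 − 1 = −24.2%: no alert, but below either assumed limit.
- Creatinine 1.10 to 1.39 is +0.29: no alert, but above every assumed limit.
- UPCR 0.49 is under the 0.5 alert but is 0.49/0.25 = 1.96 times the entry limit in 5.2, so it is unlikely to count as normal.

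The test is therefore worth keeping alongside the alert.

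**What confirming means in 8.6.2.** No text settles this, so it is an inference. Four places point to a persisting alert:

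1. Section 8.5, to which 8.5.2 refers for confirmation, says that "the clinical laboratory results meeting any of the safety monitoring criteria presented below must be confirmed by performing measurements" on new specimens.
2. Section 8.5 then judges retests against the stopping rules, not a reference range: "In general, patients who do not meet the stopping rules based upon retest may continue dosing".
3. The Amendment 3 summary describes the 8.6.2 rule as the monitoring rules once confirmed (used here only for meaning).
4. SAP 3.7.4 substitutes a better repeat for the initial value and tabulates it against the same four thresholds. That is a tabulation rule, not a dosing rule.

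**The case against.** The strongest reply is that the protocol, read as a whole, already catches the case. A repeat eGFR of 74 against a baseline of 100 itself meets an alert, so the interruption sentence applies again. Any restart requires consultation with the Medical Monitor on all relevant data, and a persisting change is relevant. Section 8.5.2 refers the reader to 8.6.2 for interruption and stopping. If 8.6.2 treats a persisting alert as confirmed, withdrawal and special-interest reporting follow. The size rests on assumed limits: at an eGFR limit of 90 few baselines qualify, and the number affected could be zero out of about 100.

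Much of this stands as mitigation. Continuation is permitted, not automatic, and the frequency is unknown. It does not remove the defect. On that reading the same repeat is negative and alert-meeting at once, and nothing says which prevails. Section 8.6.2 cannot settle it without defining confirmation. The other safeguards rely on judgment, while the written rule tells those exercising it that the test is negative.

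**Conclusion.** The concern holds and should be fixed. As written, 8.5.2 can clear a patient whose triggering change in eGFR or creatinine persists. Some overlap exists under every limit assumed above, but how wide it is depends on the laboratory's actual ranges, and the number of patients cannot be estimated from the documents. That the definition of negative does not match the two alerts is plain from the text; the conflict with 8.6.2 is the natural reading rather than stated text. The effect is on patient safety, special-interest reporting and the count of patients stopped under a rule. The primary efficacy analysis is unaffected, and so is the SAP renal abnormality table, which already uses the alert thresholds.

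**What to change.** In 8.5.2, keep the normal-limits test and add a second condition, so that a negative repeat is one taken within 7 days that is within normal limits *and no longer meets any alert criterion above*. In 8.6.2, add: *A repeat that still meets an alert criterion is confirmed.*

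Do not replace the normal-limits test. That would loosen the rule for UACR, UPCR and patients with low baseline function.

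Two clarifications are worth including. A repeat that meets no alert but is outside normal limits should stay on hold until the decision that 8.5.2 already sends to the Medical Monitor and DSMB specialist. The added condition should apply to the analytes repeated, so that a urine-only alert does not appear to require a new serum test.

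The cost is a few words in an amendment or site memo, with no new visit, sample or test. The downside is that a few more patients with good baseline function may be held or withdrawn. No patient held under the current wording would be released.
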